### 6.2.2 Exclusion Criteria

---

Retrospective cases must not meet the following exclusion criteria:

11. Enrollment into the OPTALYSE PE study

Prospective subjects must not meet any of the following exclusion criteria:

12. Clinician deems the subject high-risk for catastrophic bleeding
13. Life expectancy  $<$  one year

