## 11.4 Demographics

For each subject, year of birth, and gender are collected. In some countries, race and ethnicity are collected.

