### **13.2 Determination of Sample Size**

For retrospective cases, up to 1000 cases will be collected to capture details of PE treatment with EKOS from the time it became commercially available to the time the site was activated. For prospective, up to 500 patients will be treated to collect data on current EKOS use at up to 100 sites.

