### **13.6 Measurement of APT treatment**

APT treatment and procedure details will be summarized. Patients will be analyzed according to the APT treatment protocol they received (e.g., >6h/>24mg; 6h/12-24mg; 6h/6-12mg; 4h/4-8mg; 2h/4-8mg, other). Frequency of use of each of the APT treatment protocols before and after OPTALYSE PE results were made public will be summarized and compared using fisher's exact test.

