### 1.1 Study design

This multicenter, international registry is designed to retrospectively and prospectively collect treatment and outcome data related to pts with submassive (Intermediate-High Risk) or massive (High Risk) PE undergoing the APT treatment. Subjects are treated per Investigator's SoC and in accordance with the IFU. Patients will be categorized according to the APT treatment protocol they received.

Intermediate-High Risk PE will be defined by evidence of RV dysfunction (RV/LV  $\geq$  1.0), hemodynamic stability (normal systemic arterial blood pressure >90 mmHg), and Troponin elevation. High Risk PE will be defined by hemodynamic instability (normal systemic arterial blood pressure <90 mm Hg and/or use of vasopressors).

Retrospective case data will consist of treatment and health outcomes of consecutive patients treated with APT between January 2014 and one year prior to date of site activation.

Prospective subject data will consist of treatment and health outcomes of treated subjects since the site was activated to participate in the registry. For each treated subject enrolled, participation in the registry lasts approximately 12 months. Subjects should be followed per Investigator's SoC. Data will be collected for any echocardiograms and CTAs completed. At minimum, a health status check should be performed at 3 and 12 months. For patients with an abnormal echocardiogram post-APT treatment, an on-site visit with echocardiogram should be performed at 3 months to assess for chronic pulmonary hypertension. An echocardiogram at 12 months is also requested for all patients. Safety data should be reported through 12 months post-index procedure.

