# 1.2 Study objectives

The objectives of this registry are:

- To understand the APT treatment protocol used as SoC across institutions and document changes in practice following the OPTALYSE PE study results
- To describe the effects of varied APT protocols on long-term patient outcomes

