#### 2.4 Treatment and other medication and therapies

#### 2.4.1 Study treatment

The following APT procedure details will be summarized:

- Location of PE
- Access route
- Fluoroscopy time
- Volume of Contrast
- Ultrasound guidance?
- Time for placement of catheters (h)
- Ultrasound (h)
- Total dose/total dose per catheter
- Technical/procedural deviations
- Frequency of adjunctive therapies following APT

Patients will be categorized according to the thrombolytic dose they received. The following categories will be used:

- >24mg
- 20.1-24mg
- 12.1-20mg
- 4-12mg
- <4mg

For each category, the mean, min, and max time will be summarized. Frequency of each of the APT categories will be summarized with observed counts and percentages for each category overall, by analysis population, by region, and by the retrospective and prospective portions of the registry.

Frequency of use of each of the APT treatment protocols before and after OPTALYSE PE results were made public will also be summarized and compared using fisher's exact test.

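### The registry's only planned test, before versus after OPTALYSE, is unadjusted, and under plausible dates it largely compares retrospective with prospective patients, who enter under different criteria

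*SAP*

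**What the plan says.** The first registry objective (Protocol 5.1, SAP 1.2) includes the aim to "document changes in practice following the OPTALYSE PE study results". It is served by one test. SAP 2.4.1 takes "Frequency of use of each of the APT treatment protocols before and after OPTALYSE PE results were made public" and says that this "will also be summarized and compared using fisher's exact test". Protocol 13.6 has the same plan, "before and after OPTALYSE PE results were made public will be summarized and compared using fisher's exact test", and Protocol 13.1 repeats it. No stratification, covariate, restriction to common criteria, analysis population or cut date is stated for the test. Everything else in the plan is descriptive.

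**Time windows.** Retrospective cases are consecutive patients "treated with APT between January 2014 and one year prior to date of site activation" (SAP 1.1; Protocol 5.2 gives 1 January 2014). Prospective data start at site activation, so each site has a 12-month gap with no cases. Protocol 13.2, however, describes retrospective collection as running "from the time it became commercially available to the time the site was activated", and SAP 2.9 also ends it at activation.

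**Entry criteria (Protocol 6.2).** Both portions require RV/LV of at least 1.0, symptoms of at most 14 days and raised troponin. Only the prospective portion adds age limits, consent, the exclusion "Clinician deems the subject high-risk for catastrophic bleeding" and an exclusion for life expectancy under one year. Only the retrospective portion excludes OPTALYSE participants.

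**What is already shown by portion.** SAP 2.3.2 summarises baseline data by portion, and SAP 2.4.1 does the same for dose-category frequencies. Neither is crossed with before/after.

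**The concern.** The test is split by calendar time, but calendar time is tied to the portion of the registry, and the portion determines who may enter. Age, perceived bleeding risk and short life expectancy can plausibly influence the regimen a physician chooses, which is the variable being tested. Such patients can appear in 'before' and are largely screened out of 'after'. A significant result could then reflect eligibility and not practice, and a null result could hide a real change. This matters because the comparison is the plan's only inferential statement and bears directly on the first objective.

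**Working it through.** **There is no planned figure to reproduce.** The sample sizes (up to 1000 retrospective, up to 500 prospective) come from expected enrolment. No alpha, power or effect size is given. A two-sided 5% level is assumed below.

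**Step 1: how closely the two labels coincide.** The Protocol reference list cites OPTALYSE as a 2017 presentation and a July 2018 paper, and SAP section 1 rests on a protocol version of May 2018. Assumptions:
- release in January, September or December 2017, or July 2018;
- all sites activated together, at one of six dates from January 2018 to July 2020 in six-month steps;
- uniform accrual, with 1000 retrospective cases from January 2014 to activation minus 12 months, and 500 prospective patients over the planned 24 months from activation.

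Worked examples:
- Release September 2017, activation January 2019: the retrospective window is 48 months, of which 4 fall after release. 4/48 = 8.3%, about 83 cases. Agreement = (917 + 500)/1500 = 94%.
- Release January 2017, activation July 2020: 30 of 66 months fall after release, 45.5% or about 455 cases. Agreement = (545 + 500)/1500 = 70%. The 'after' group is 500/955 = 52% prospective.
- Release July 2018, activation January 2018: 6 of the 24 prospective months precede release, so 125 prospective patients are 'before'. The 'before' group is 1000/1125 = 89% retrospective.

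Over all 24 pairs, agreement is 70% to 100%, 'before' is wholly retrospective in 23 pairs (89% in the other), and 'after' is 52% to 100% prospective. With release from September 2017 to July 2018 and activation from January 2018 to January 2020, agreement is 82% to 100%.

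**Step 2: what a case-mix difference does to the test.** Let a share f of retrospective cases fail the prospective criteria, with use u of a given regimen category against 30% in everyone else. With complete alignment and no practice change:

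before − after = f × (u − 30%)

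Rejection rates are for Fisher's exact test at 1000 versus 500. They sum the binomial probabilities of all tables with p < 0.05; simulation with 2000 to 4000 runs per setting agrees to within about two points.

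| f | u | Spurious difference (points) | False rejection | True 10-point rise appears as | Power |
|---|---|---|---|---|---|
| 0 | – | 0 | 5% | 10 | 97% |
| 5% | 50% | 1 | 6% (7% simulated) | 9 | 93% |
| 10% | 60% | 3 | 21% | 7 | 75% |
| 20% | 55% | 5 | 49% | 5 | 46% |
| 20% | 60% | 6 | 64% | 4 | 32% |
| 10% | 10% | −2 | 12% | 12 | over 99% |

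Hand check of the third row: p = 0.33 and 0.30, pooled 0.32. SE under the null = √(0.32 × 0.68 × (1/1000 + 1/500)) = 0.0255. SE under the alternative = √(0.33 × 0.67/1000 + 0.30 × 0.70/500) = 0.0253. (0.03 − 1.96 × 0.0255)/0.0253 = −0.79, which gives 21%.

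The last row reverses the direction: the excluded patients use the category less, and a true rise is exaggerated. Raising u to 70% at f = 20% gives 8 points and about 86%, but nothing in the documents points to so extreme a value.

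**Step 3: incomplete alignment.** If f and u are stable over time, the spurious difference is multiplied by (retrospective share of 'before' − retrospective share of 'after'). At the weakest pair this is 1 − 0.48 = 0.52, so 3 points becomes about 1.6 and 6 becomes about 3.1. The bias shrinks but stays.

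**Step 4: what can be matched.** Protocol 11.4 says "For each subject, year of birth, and gender are collected", and Protocol 8.1 lists demographics for retrospective cases, so age can be matched, to within a year. Bleeding-risk judgement and life expectancy are not among the retrospective data in Protocol 8.1 to 8.4, and consent has no retrospective counterpart.

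**The case against.** The strongest reply is that this is a descriptive registry. A reader might infer that the plan attributes the whole before/after difference to OPTALYSE. It does not: frequencies are to be summarised and compared, and the objective speaks of change following the results, which is wording about time. That stands. The weakness is that the test cannot separate the causes, not that the plan claims it can.

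A reader might also take it as established that 'before' means retrospective and 'after' means prospective. The documents do not establish this, because neither the release date nor activation dates are given. At one end of the assumed range, almost half of 'after' is retrospective. The alignment is an inference, though it is substantial over the whole range.

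The size is open too. No document gives f, u or the 30% base, and the arithmetic uses one category against the rest where SAP 2.4.1 has five dose categories. The shared criteria, and the fact that every patient was selected for APT, limit the case-mix difference. With a small f the effect is close to nothing.

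The one-year gap is not a source of case-mix bias in itself. For activation around mid-2018 it removes the year around publication, so a site could not show when practice changed.

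Finally, the by-portion tables let a reader see an imbalance, but they do not carry it into the before/after comparison. Running the test in the efficacy population would not help if, as reads naturally, eligibility there means each portion's own criteria.

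**Conclusion.** The point holds as a limit on interpretation that the plan can reduce at little cost. The text itself establishes an unadjusted test as the only one named, entry criteria that differ by portion, and a per-site gap of one year. That the before/after split largely follows the portions rests on assumed dates.

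The direction of the bias is unknown, and the rates in the table are illustrations, not estimates. They show that the effect could be negligible or could dominate: with equal case mix, 1000 versus 500 detects about 7 points from 30% with 80% power, and the spurious differences considered reach that order.

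A reader might infer that restricting to common criteria would restore a clean comparison with full power. The listed retrospective data do not support that. Only age can be applied, so the gain is partial and cannot be quantified from the documents.

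The retrospective end date in Protocol 13.2 and SAP 2.9 is a separate inconsistency. It contradicts Protocol 5.2 and 6.2.1 and SAP 1.1 whatever view is taken of the confounding.

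**What to change.** In SAP 2.4.1:

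1. State one fixed calendar date on which OPTALYSE results count as public.
2. Add the before/after comparison with retrospective cases restricted to the prospective age limits, reported alongside the all-patient test. First reconcile the lower limit, which includes age 18 in the Protocol synopsis but not in 6.2.1, and give a rule for age when only the year of birth is held.
3. Cross-tabulate regimen frequency by before/after and portion, and by calendar half-year and portion.
4. Treat any before/after comparison within the retrospective portion as supportive only. It holds entry criteria constant but may have few or no 'after' cases: none if release is July 2018 and sites activate by July 2019, about 83 of 1000 for September 2017 and January 2019, and about 267 for September 2017 and January 2020.
5. State that bleeding risk, life expectancy and consent cannot be matched from the listed retrospective data, that residual confounding therefore remains, and that the Fisher result describes change over time and is not attributable to OPTALYSE.

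Separately, correct Protocol 13.2 and SAP 2.9 so that the retrospective window ends one year before site activation, as in Protocol 5.2 and 6.2.1 and SAP 1.1.

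The cost is SAP text, a one-line protocol correction, extra tables and a somewhat smaller restricted set. No new data are needed. Label: cheap improvement.

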### **5.1 Objectives**

The objectives of this registry are:

- To understand the APT treatment protocol used as SoC across institutions and document changes in practice following the OPTALYSE PE study results
- To describe the effects of varied APT protocols on long-term patient outcomes

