## **13. STATISTICAL CONSIDERATIONS**

### **13.1 Statistical Analysis**

The statistical analysis plan (SAP) will be a separate document finalized prior to data analysis. The SAP will be updated as required, in association with any protocol amendments. The plan will include detailed descriptions of analysis methods, tables, listings and figures and will describe statistical programming considerations.

For descriptive statistics, continuous data (e.g., age) will be summarized with n, mean, median, standard deviation, minimum and maximum and categorical data (e.g., gender) will be summarized with observed counts and percentages for each category.

Patients will be analyzed according to the APT treatment protocol they received (i.e. duration of treatment and dose, type of fluid received). Frequency of use of each of the APT treatment protocols before and after OPTALYSE PE results were made public will be summarized and compared using fisher's exact test.

Each outcome measure will be summarized for the full registry population as well as separately by the different APT treatment protocols, including 95% confidence intervals. Additionally, outcome measures will be summarized by the following subgroups: submassive and massive PE, each region, and by the retrospective and prospective portions of the registry.

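### The before/after comparison in SAP 2.4.1 gives counts, percentages and a Fisher p-value, but no estimate of change with an interval and no comparison of infusion time

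*SAP*

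**What the plan says.** The first objective (Protocol 5.1, SAP 1.2) is to understand the treatment protocols in use and to "document changes in practice following the OPTALYSE PE study results".

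The analysis is in SAP 2.4.1. On categories it says: "Patients will be categorized according to the thrombolytic dose they received". The bands are >24, 20.1-24, 12.1-20, 4-12 and <4 mg. On duration: "For each category, the mean, min, and max time will be summarized". Band frequencies are given as counts and percentages. How often each protocol was used "before and after OPTALYSE PE results were made public will also be summarized and compared using" Fisher's exact test. Total dose and ultrasound hours are both on the list of procedure details to be summarized.

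Protocol 13.1 and 13.6 name the same test. Protocol 13.6 gives example categories that cross duration with dose: >6h/>24mg, 6h/12-24mg, 6h/6-12mg, 4h/4-8mg, 2h/4-8mg and other.

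Fisher's exact test is the only hypothesis test in either document. Neither states its significance level or a power for it. The 95% intervals in Protocol 13.1 are for the outcome measures, and use of treatment protocols is not among the ten measures in Protocol 5.3.

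**The concern.** To record a change in practice is to say what moved, in which direction, by how much and with what uncertainty. The planned table and p-value cover part of this. A reader can subtract one percentage from another, but gets no interval and no statement of how far dose in mg or time in hours moved.

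Duration is the larger gap. OPTALYSE PE varied treatment time as well as dose (Protocol 4.3). The SAP bands use dose only, and time is summarized within band with no split by period. A registry in which infusions became much shorter at similar doses could report no change.

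There is also a question of efficiency. The five bands are ordered, and an unordered test does not use the order.

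**Working it through.** **1. What the tested table can see.** Protocol 4.3 lists the OPTALYSE arms as 8 mg/2 h, 8 mg/4 h, 12 mg/6 h and 24 mg/6 h. Taking these as total doses (an assumption), the SAP bands place them as follows:

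| Arm | SAP band |
|---|---|
| 8 mg/2 h | 4-12 mg |
| 8 mg/4 h | 4-12 mg |
| 12 mg/6 h | 4-12 mg |
| 24 mg/6 h | 20.1-24 mg |

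Three regimens with durations from 2 h to 6 h share one band. Likewise three of the example categories in Protocol 13.6 (6h/6-12mg, 4h/4-8mg, 2h/4-8mg) lie inside 4-12 mg. If every patient in that band moved from 6 h to 2 h, all counts in the 2 x 5 table would stay the same, and so would the p-value.

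**2. What an interval would add.** Suppose use of the 4-12 mg band rises from 18% of 1,000 to 23% of 500 (assumed values). The difference is 5 points. Its standard error is √(0.18×0.82/1000 + 0.23×0.77/500) = √(0.0001476 + 0.0003542) = 0.0224. The 95% interval is 5 ± 1.96×2.24, or 0.6 to 9.4 points. The plan as written does not produce this.

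**3. Power, unordered against ordered.** The documents give no power figure to reproduce, so every input here is assumed:
- 1,000 before and 500 after. These are the retrospective and prospective maxima in SAP 2.9, used as stand-ins for the two periods.
- Baseline 25/25/30/18/2% from the highest to the lowest band.
- Two-sided 5%, and one 2 x 5 table.
- A shift that multiplies the odds of being at or below each cut by a common odds ratio. At 1.3, for example, 12 mg or less goes from 20% (odds 0.25) to odds 0.325, which is 24.5%.

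I simulated 20,000 tables per setting (simulation error below 0.4 points). The unordered test is the 4-df chi-square. In a separate run of 600 tables per setting it agreed with Monte Carlo Fisher p-values to within about 2 points. The ordered test is the linear trend test; the tie-corrected Wilcoxon test gave the same power to within 2 points.

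| Odds ratio | Unordered | Ordered | Loss (points) |
|---|---|---|---|
| 1.2 | 28% | 45% | 17 |
| 1.3 | 55% | 76% | 21 |
| 1.4 | 80% | 93% | 13 |
| 1.5 | 93% | 99% | 6 |
| 2 | 100% | 100% | 0 |

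With 200 before and 100 after, power is 13% against 22% at odds ratio 1.3 (9 points) and 28% against 45% at 1.5 (17 points).

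**4. A redistribution without one direction.** The OPTALYSE arms fall in two bands that are not adjacent. If regimens like these were adopted, patients could leave the >24 mg and 12.1-20 mg bands for the other two. With the same baseline and group sizes, and five percentage points leaving each of those two bands:

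| Where the ten points go | Unordered | Ordered |
|---|---|---|
| Split equally between 20.1-24 and 4-12 mg | 86% | 38% |
| All to 20.1-24 mg | 94% | 5% |
| All to 4-12 mg | 98% | 90% |

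In all three cases the unordered test is the more powerful one.

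**The case against.** The strongest reply is that Fisher's exact test suits the question asked. The objective names no direction. The registry is descriptive, and its size rests on expected enrollment with no power claim (Protocol synopsis). The protocol's duration-by-dose groups include an open category and have no single order, so an unordered test is natural for them. The largest 48-hour RV/LV change in Protocol 4.3 is in the 24 mg arm (-0.32), so those results do not clearly push all practice towards lower dose. Step 4 shows that an ordered test can miss a real change. All of this stands, and it rules out replacing Fisher's exact test.

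It is also fair that the frequencies are to be summarized as well as tested, so direction and rough size can be read from the percentages. What remains missing is an interval and any before/after comparison of time.

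If the protocols in the Fisher sentence mean the groups in Protocol 13.6, duration does enter the table. But SAP 2.4.1 defines only dose bands, and the Protocol 13.6 groups are offered as examples.

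A reader might infer that the power loss is worse within sites, regions or portions. The figures do not show this in general: at odds ratio 1.3 it is 9 points at 200/100 and 21 at 1,000/500. It is larger in the smaller groups only for bigger shifts (17 against 6 points at 1.5).

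**Conclusion.** The point holds as a gap in reporting. With the SAP's dose-only bands, SAP 2.4.1 plans no before/after estimate with an interval and no before/after comparison of infusion time. The first part needs no assumption. The example of a hidden change in time needs the OPTALYSE doses to be totals.

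A reader might go further and infer that Fisher's exact test is the wrong test or leaves the objective underpowered. The documents do not support that. The loss of 13 to 21 points applies to a modest, consistent shift to lower dose at odds ratios 1.2 to 1.4. It is about 6 points at 1.5, nil at 2, and reversed for the redistributions in step 4. These figures rest on an assumed baseline, significance level and shift, and on a before/after split that the documents do not fix, since no date is given for when the results became public. Clustering of practice by site was not modelled.

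This is an inexpensive improvement. It is not a flaw that invalidates the planned analysis.

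**What to change.** In SAP 2.4.1:

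- Keep Fisher's exact test as the general comparison of category use.
- Add a before/after comparison of total dose (mg) and of infusion or ultrasound time (h) as continuous variables: Wilcoxon rank-sum, or van Elteren if stratified, with the Hodges-Lehmann difference and its 95% interval. Show medians and quartiles by period as well, because doses and times are likely to cluster on a few values and the Hodges-Lehmann figure may then be coarse.
- Add before/after differences in category percentages with 95% intervals.
- Label these additions as descriptive.

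The cost is SAP wording and a few more table rows. SAP 2.4.1 already lists total dose and ultrasound hours, so no new data are needed. The downside is a little more analysis and a few more comparisons, which the descriptive label addresses.
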